The study is designed as a 16 week study and consists of 6 distinct visits as described above. Screening will consist of a 1a and optional 1b visit. Visit 1b is optional. It exists so that the subject can pick up the Empatica E4 wrist device that cannot be given until their monocyte profile is known. Visits 3 and 5 will also be split into part a and b. Visit b will be optional. If the subject chooses to participate, visit b is when the subject returns the wrist device.

Study Treatments

Apremilast will be dispensed in dose titration cards at Visit 2. At Visit 3, apremilast tablets will be supplied in high density polyethylene (HDPE) bottles containing approximately 60 tablets each.

Overview of Efficacy Assessments

Primary Clinical Assessment

The primary clinical assessment will be Psoriasis Area and Severity Index (PASI) scores.

Additional Clinical Assessments

- Static Physician's Global Assessment (sPGA)
- Body Surface Area (BSA)
- Subject's Assessment of Pruritus VAS
- Subject's Assessment of Skin Discomfort/Pain VAS
- Subject Global Assessment of Psoriasis Disease Activity VAS
- Subject's Assessment of Joint Pain VAS
- Subject Global Assessment of Psoriatic Arthritis Disease Activity VAS
- Health Related Quality of Life (HRQoL) questionnaires:
 - Dermatology Life Quality Index (DLQI)
 - Work Productivity and Activity Impairment Questionnaire: Psoriasis (WPAI: PSO)

Overview of Safety Assessments

Safety Assessments

- Adverse events (AE)
- Physical examinations
- Vital signs
- Clinical laboratory tests
- Evaluation of psoriasis flare or rebound.

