Psoriasis Area Severity Index scores range from 0 to 72, with higher scores reflecting greater disease severity [50]. Erythema, thickness, and scaling are scored on a scale of 0 (none) to 4 (very severe) on 4 anatomic regions of the body: head, trunk, upper limbs, and lower limbs. Degree of involvement on each of the 4 anatomic regions is scored on a scale of 0 (no involvement) to 6 (90% to 100% involvement). The total qualitative score (sum of erythema, thickness, and scaling scores) is multiplied by the degree of involvement for each anatomic region and then multiplied by a constant. These values for each anatomic region are summed to yield the PASI score.

- **Body Surface Area (BSA)**

BSA is a measurement of involved skin. The overall BSA affected by psoriasis is estimated based on the palm area of the subject's hand (entire palmar surface or "handprint"), which equates to approximately 1% of total body surface area.

- **Physician Global Assessments (PGAs)**

- **Static Physician's Global Assessment (sPGA)**

The sPGA is the assessment by the Investigator of the overall disease severity at the time of evaluation. The sPGA is a 5-point scale ranging from 0 (clear) to 4 (severe), incorporating an assessment of the severity of the three primary signs of the disease: erythema, scaling and plaque elevation. When making the assessment of overall severity, the Investigator should factor in areas that have already been cleared (i.e. have scores of 0) and not just evaluate remaining lesions for severity, i.e., the severity of each sign is averaged across all areas of involvement, including cleared lesions. Areas of cleared lesions may be directly assessed if outlines of the original lesions can be directly visualized (e.g., residual hyperpigmentation) or, if not, by factoring in the minimum BSA for inclusion in the study (i.e., at least 10%). In other words, if there are small lesions of mild severity covering 1% BSA, but there are cleared lesions covering 9+% BSA, over 90% of the severity is clear; this should be integrated into the final assessment. In the event of different severities across signs of psoriasis, the sign that is the predominant feature of psoriasis should be used to help determine the sPGA score. See Appendix B for grading criteria.

- **Health Assessment Questionnaire Disability Index (HAQ-DI)**

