6.2. Inclusion Criteria

Subjects must satisfy the following criteria to be enrolled in the study:

1. Males or females, ≥ 18 and ≤ 65 years of age at the time of signing the informed consent document.
2. Understand and voluntarily sign an informed consent document prior to any study related assessments/procedures being conducted.
3. Able to adhere to the study visit schedule and other protocol requirements.
4. Patients must exhibit AM-endotype psoriasis patients, identified by elevated ($>150\%$ of normal) levels of any one of the following criteria:
 - Intermediate (CD14⁺⁺CD16⁺) monocytes, OR
 - Circulating monocyte doublets, OR
 - Circulating monocyte-platelet aggregates (MPA).
5. Diagnosis of chronic plaque psoriasis for at least 12 months prior to Screening.
6. Have moderate to severe plaque psoriasis at Screening and Baseline as defined by
 - a. BSA $\geq 5\%$
 - b. sPGA ≥ 3 (moderate to severe)
7. Must be a candidate for phototherapy and systemic (including Otezla) therapy.
8. Must be in good health (except for psoriasis) as judged by the Investigator, based on medical history and physical examination.
9. Subject must have completed 5-7 days of successful Empatica device data collection. (Optional: Only if subject chooses to participate)
10. Subject must have consistent internet access and the ability to successfully download the Empatica data manager user interface. (Optional: Only if subject chooses to participate)

11. Females of childbearing potential (FCBP) must have a negative pregnancy test at Screening and Baseline. While on investigational product and for at least 28 days after taking the last dose of investigational product, FCBP who engage in activity in which conception is possible must use one of the approved contraceptive options described below:

Option 1: Any one of the following highly effective methods: hormonal contraception (oral, injection, implant, transdermal patch, vaginal ring); intrauterine device (IUD); tubal ligation; or partner's vasectomy;

OR

Option 2: Male or female condom (latex condom or non-latex condom NOT made out of natural [animal] membrane [for example, polyurethane]); PLUS one additional barrier method: (a) diaphragm with spermicide; (b) cervical cap with spermicide; or (c) contraceptive sponge with spermicide.

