Other outcomes such as PASI will be analyzed similarly. Note that we will also correlate change in our abnormally elevated monocyte markers at various time points with change in PASI, to explore possible mechanistic associations. For a two-sided Wilcoxon test with Type I error of 0.05, power is 0.80 if the effect size is 0.60 or greater (assuming an underlying normal distribution). For 20% median reduction, as long as standard deviation of percent change is not larger than 33%, we will have effect size of at least 0.60. These are plausible assumptions given our prior work on treatment related monocyte reductions [40].

Because the study is not a randomized trial, any subjects that are required to be placed on rescue therapy, but continue in the study will have any data after rescue treated as missing values and these missing values will be imputed from the average of all subjects completed. Alternatively if rescue therapy is required for > 50% of the patients, then these individuals would be analyzed as a separate cohort of patients and will not be analyzed in the grouped data.

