Appendix B: Physician's Global Assessments (PGA)

Static Physician's Global Assessment (sPGA)

Score	Category	Description
0	Clear	
Plaque elevation = 0 (no elevation over normal skin)
 
Scaling = 0 (no evidence of scaling)
 
Erythema = 0 (except for residual hyperpigmentation/hypopigmentation)

1	Almost Clear	
Plaque elevation = ± (possible but difficult to ascertain whether there is a slight elevation above normal skin)
 
Scaling = ± (surface dryness with some desquamation)
 
Erythema = ± (faint, diffuse pink or slight red coloration)

2	Mild	
Plaque elevation = slight (slight but definite elevation, typically edges are indistinct or sloped)
 
Scaling = fine (fine scale partially or mostly covering lesions)
 
Erythema = mild (light red coloration)

3	Moderate	
Plaque elevation = marked (marked definite elevation with rough or sloped edges)
 
Scaling = coarser (coarser scale covering most or all of the lesions)
 
Erythema = moderate (definite red coloration)

4	Severe	
Plaque elevation = marked (marked elevation typically with hard or sharp edges)
 
Scaling = coarser (coarse, non-tenacious scale predominates covering most or all of the lesions)
 
Erythema = severe (very bright red coloration)

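### The sPGA fallback rule gives the BSA entry minimum as 10%, but inclusion criterion 6a sets it at 5%, so clearing can be over-credited in patients who entered below 10%

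*Combined protocol and SAP*

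**What the plan says.** Section 5 (sPGA) asks the investigator to average the severity of each sign over all involved skin, counting cleared lesions as zero. It gives two routes for cleared skin. The first is direct: "Areas of cleared lesions may be directly assessed if outlines of the original lesions can be directly visualized". If outlines cannot be seen, the rater proceeds "by factoring in the minimum BSA for inclusion in the study (i.e., at least 10" percent). The example that follows rests on the same figure: "if there are small lesions of mild severity covering 1% BSA, but there are cleared lesions covering 9+% BSA", then "over 90% of the severity is clear; this should be integrated into the final assessment".

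Section 6.2, criterion 6, reads "Have moderate to severe plaque psoriasis at Screening and Baseline as defined by" and lists two conditions: 6a, BSA of 5% or more, and 6b, sPGA of 3 or more. This is the only BSA threshold for entry in the document.

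The Protocol Summary lists sPGA under "Additional Clinical Assessments", and PASI is the primary clinical assessment. Section 9.1 has no analysis specific to sPGA, only the general line "Other outcomes such as PASI will be analyzed similarly".

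**The concern.** The rating instruction cites the protocol's own entry criterion and misstates it. The assumed original area is the denominator of the average that the rater is asked to form, so the figure matters to the rule. A patient who entered with 5% to under 10% BSA meets criterion 6a but never had 10% of skin involved. For that patient the printed figure counts never-affected skin as cleared, and the error always favours improvement, in an open-label study whose treated patients have no comparator arm.

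A rater who looks up criterion 6a would use 5%. Two raters could therefore use different bases for the same patient, and Section 6.1 names three enrolling locations. What is at stake is the consistency of sPGA at visits where the fallback is used.

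**Working it through.** **Inputs.** Printed fallback base: 10% (Section 5, sPGA). Entry minimum: 5% (Section 6.2, criterion 6a). Residual area in the plan's example: 1% BSA (Section 5, sPGA). Assumption: the remaining lesions lie within the area involved at entry.

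**Formula.** With residual area r and original area B, both in % BSA, the cleared share is 1 − r/B.

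**The plan's own example.** With 1% left and 9% cleared, 9/(9 + 1) = 90%. With slightly more cleared, say 9.5%, 9.5/10.5 = 90.5%. The stated figure of over 90% therefore follows from the 10% base.

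**Printed base against the patient's own entry area, 1% left.** The printed base gives (10 − 1)/10 = 90% whatever the entry area.

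| Entry BSA | Share of own area cleared | Over-credit (percentage points) |
|---|---|---|
| 5% | 4/5 = 80.0% | 10.0 |
| 6% | 5/6 = 83.3% | 6.7 |
| 7% | 6/7 = 85.7% | 4.3 |
| 8% | 7/8 = 87.5% | 2.5 |
| 9% | 8/9 = 88.9% | 1.1 |

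In general the over-credit is r × (1/B − 1/10). It is positive for any entry area below 10% with disease remaining, and zero at 10%.

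**Two raters, one using 10% and one using criterion 6a's 5%.** The comparison is (10 − r)/10 against (5 − r)/5, a difference of r/10, or 10 points per 1% BSA left: 90 v 80% with 1% left, 80 v 60% with 2%, 70 v 40% with 3%, and 60 v 20% with 4%. Both thresholds are minimums, so these figures show what happens when each is used as the base.

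**Link to the grade.** For mild residual lesions (grade 2) over 1% BSA, the area average is 2 × 1/5 = 0.4 on the 5% base and 2 × 1/10 = 0.2 on the 10% base. Neither value is a grade. Appendix B defines grades by verbal descriptors (grade 3 elevation, for example, is "marked definite elevation with rough or sloped edges"), and clearing enters by judgement. The arithmetic therefore cannot be turned into a change of sPGA score.

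**The case against.** The strongest reply is that the effect depends on several conditions and cannot be measured from the documents. It requires outlines that are no longer visible, entry below 10% BSA, some remaining disease, and a rater who follows the printed figure rather than criterion 6a or the BSA already on file. The cleared share of area is not itself recorded or analysed, and a different share need not change the grade. All of this stands, and it is why the point is minor.

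A second reply is that the rule says at least 10% and the example says 9+%, so 10% is a floor and not a fixed base. That removes any claim of under-crediting in patients who entered above 10%, and none is made. It does not help below 10%, where a floor of 10% is still higher than the area the patient had.

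A third reply is that the documents do not show which threshold was intended, and that reconciling the sections does not strictly require a new rating rule. Both are fair. Basing the fallback on the subject's own BSA is a preference, but it works whichever threshold was meant.

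**Conclusion.** The contradiction is certain: both statements are current protocol text, and no other section reconciles them. Used as printed, the 10% figure over-credits cleared area in patients who entered at 5% to under 10% BSA, by 1.1 to 10.0 percentage points with 1% left and entry at 9% down to 5%, and by more with more disease remaining. This assumes that the remaining lesions lie within the entry area.

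The consequence for sPGA is unknown, because the documents state neither the share of patients entering below 10% nor how often the fallback is used. The monocyte primary outcome, PASI and the power statement are unaffected. Severity is minor; high confidence applies to the contradiction, not to any shift in sPGA scores.

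**What to change.** Reconcile the sPGA text in Section 5 with criterion 6a in Section 6.2. The preferred change is to delete the 10% figure and have the rater, when outlines cannot be seen, factor in the subject's own BSA at Visit 2A. The example should change with it: if BSA was 5% at Visit 2A and mild lesions now cover 1%, then 80% of the original area is clear.

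Making the fallback figure and example agree with criterion 6a would also end the contradiction, but it is second best. Treated as a fixed base, 5% under-credits patients who entered with more: for entry at 10% with 1% left it gives 80% against a true 90%.

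The cost is a short amendment approved by Amgen, with IRB/EC approval unless it is classed as administrative (Section 13.5), plus a reminder to raters. The Table of Events already schedules BSA at Visit 2A, so no new measurement is needed. If any subjects have been rated under the present wording, which the documents do not say, the change of rule should be noted when sPGA is reported.

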6. STUDY POPULATION

6.1. Number of Subjects and Sites

Approximately 55 subjects will be enrolled at UHCMC, University Hospitals Dermatology Fairlawn, or Wright State University Boonshoft School of Medicine. UHCMC investigational pharmacy will coordinate investigational product (IP) shipment to WSUSOM investigational pharmacy. Goal is to have 25 psoriasis patients aged 18-65 years old and 10 healthy controls complete the trial (35 total). Total enrollment of 55 is to account for screen fails and early terminations.

6.2. Inclusion Criteria

Subjects must satisfy the following criteria to be enrolled in the study:

1. Males or females, ≥ 18 and ≤ 65 years of age at the time of signing the informed consent document.
2. Understand and voluntarily sign an informed consent document prior to any study related assessments/procedures being conducted.
3. Able to adhere to the study visit schedule and other protocol requirements.
4. Patients must exhibit AM-endotype psoriasis patients, identified by elevated ($>150\%$ of normal) levels of any one of the following criteria:
 - Intermediate (CD14⁺⁺CD16⁺) monocytes, OR
 - Circulating monocyte doublets, OR
 - Circulating monocyte-platelet aggregates (MPA).
5. Diagnosis of chronic plaque psoriasis for at least 12 months prior to Screening.
6. Have moderate to severe plaque psoriasis at Screening and Baseline as defined by
 - a. BSA $\geq 5\%$
 - b. sPGA ≥ 3 (moderate to severe)
7. Must be a candidate for phototherapy and systemic (including Otezla) therapy.
8. Must be in good health (except for psoriasis) as judged by the Investigator, based on medical history and physical examination.
9. Subject must have completed 5-7 days of successful Empatica device data collection. (Optional: Only if subject chooses to participate)
10. Subject must have consistent internet access and the ability to successfully download the Empatica data manager user interface. (Optional: Only if subject chooses to participate)

11. Females of childbearing potential (FCBP) must have a negative pregnancy test at Screening and Baseline. While on investigational product and for at least 28 days after taking the last dose of investigational product, FCBP who engage in activity in which conception is possible must use one of the approved contraceptive options described below:

Option 1: Any one of the following highly effective methods: hormonal contraception (oral, injection, implant, transdermal patch, vaginal ring); intrauterine device (IUD); tubal ligation; or partner's vasectomy;

OR

Option 2: Male or female condom (latex condom or non-latex condom NOT made out of natural [animal] membrane [for example, polyurethane]); PLUS one additional barrier method: (a) diaphragm with spermicide; (b) cervical cap with spermicide; or (c) contraceptive sponge with spermicide.

The female subject's chosen form of contraception must be effective by the time the female subject is randomized into the study (for example, hormonal contraception should be initiated at least 28 days before randomization)

Male subjects (including those who have had a vasectomy) who engage in activity in which conception is possible must use barrier contraception (male latex condom or non-latex condom NOT made out of natural [animal] membrane [for example, polyurethane]) while on investigational product and for at least 28 days after the last dose of investigational product.

6.3. Exclusion Criteria

The presence of any of the following will exclude a subject from enrollment:

1. Other than psoriasis, history of any clinically significant (as determined by the Investigator) cardiac (clinically advanced cardiovascular disease including; Stent, past history of MI, thrombotic event or arterial calcification), endocrine, pulmonary, neurologic, psychiatric, hepatic, renal, hematologic, immunologic disease, or other major uncontrolled disease.
2. Any condition, including the presence of laboratory abnormalities, which would place the subject at unacceptable risk if he/she were to participate in the study.
3. Any condition, including other inflammatory diseases or dermatologic conditions that confound the ability to interpret data from the study.
4. Prior history of suicide attempt at any time in the subject's life time prior to screening or randomization, or major psychiatric illness requiring hospitalization within the last 3 years.
5. Pregnant or breast feeding.
6. Have failed more than 3 systemic agents for treatment of psoriasis.
7. History of allergy to any component of apremilast.
8. Had a serious infection (including, but not limited to, hepatitis, pneumonia, sepsis, cellulitis, meningitis or pyelonephritis) or have been hospitalized for an infection. Subject must be cured of infection > 4 weeks before Screening.

9. Have a history of, or ongoing, chronic or recurrent infectious disease, including, but not limited to, chronic renal infection, chronic chest infection (e.g., bronchiectasis), sinusitis, recurrent urinary tract infection (e.g., recurrent pyelonephritis, chronic nonremitting cystitis), an open, draining, or infected skin wound or ulcer.
10. Had a Bacillus Calmette-Guérin (BCG) vaccination within 1 year prior to screening.
11. History of positive human immunodeficiency virus (HIV), or have congenital or acquired immunodeficiency (e.g., common variable immunodeficiency disease).
12. Active substance abuse or a history of substance abuse within 6 months prior to Screening.
13. Bacterial infections requiring treatment with oral or injectable antibiotics, or significant viral or fungal infections, within 4 weeks of Screening. Any treatment and cure for such infections must have been completed at least 4 weeks prior to Screening.
14. Malignancy or history of malignancy, except for:
 - a. treated [i.e., cured] basal cell or squamous cell in situ skin carcinomas;
 - b. treated [i.e., cured] cervical intraepithelial neoplasia [CIN] or carcinoma in situ of the cervix with no evidence of recurrence within the previous 5 years.
15. Topical therapy within 2 weeks of study entry (including, but not limited to, topical corticosteroids, retinoids or vitamin D analog preparations, tacrolimus, pimecrolimus, or anthralin/dithranol). Exceptions: low-potency corticosteroids will be allowed as background therapy and restricted to treatment of the face, axillae, and groin in accordance with the manufacturers' suggested usage during the course of the study (this restricted usage should be documented). Subjects with scalp psoriasis will be permitted to use coal tar shampoo and/or salicylic acid scalp preparations on scalp lesions. An unmedicated skin moisturizer (e.g. Eucerin[®]) will be also permitted for body lesions only. Subjects should not use these topical treatments within 24 hours prior to the clinic visit.
16. Systemic therapy for psoriasis within 4 weeks prior to study entry (including, but not limited to, cyclosporine, corticosteroids, methotrexate, retinoids, mycophenolate, thioguanine, hydroxyurea, sirolimus, sulfasalazine, azathioprine, and fumaric acid esters).
17. Use of phototherapy within 4 weeks prior to study entry.
18. Use of any investigational drug within 4 weeks prior to study entry, or 5 pharmacokinetic/pharmacodynamic half-lives, if known (whichever is longer).
19. Prolonged sun exposure or use of tanning booths or other ultraviolet (UV) light sources.
20. Prior treatment with Apremilast
21. Inability to wash out from biologics (e.g., TNF inhibitors IL-17 inhibitors, IL-12/23 inhibitors, for 8 weeks).

7. DESCRIPTION OF STUDY TREATMENTS

7.1. Description of Investigational Product(s)

7.1.1. Description of Apremilast

The chemical name of apremilast (CC-10004, Otezla) is acetamide, N-[2-[(1S)-1-(3-ethoxy-4-methoxyphenyl)-2-(methylsulfonyl)ethyl]-2,3-dihydro-1,3-dioxo-1H-isoindol-4-yl].

Apremilast will be provided as 10, 20, or 30 mg tablets in blister cards for titration purposes (see Appendix N). Apremilast will be provided as 30 mg tablets in HDPE bottles (approximately 60tablets) with child-resistant caps for routine dosing.

7.1.2 Treatment Administration and Schedule

Apremilast

Investigational product tablets will be taken orally twice daily, approximately 12 hours apart, without restriction of food or drink. To attempt to mitigate potential mild to moderate headache and gastrointestinal (GI) adverse events (primarily nausea), dose titration will be implemented in this study at specific times.

Dosing

During Week 0 (Days 1-7), subjects will be dispensed blister cards with standardized dosing of apremilast tablets.

